5.8 Duration of Study Participation

Participants may be removed from the study as a whole at any time at their own request, or they may be withdrawn at the discretion of the investigator for safety, behavioral or administrative reasons. The reason(s) for discontinuing study participation should be documented and may include:

- Completion of 12 months of active follow up after the end of protocol treatment
- Disease progression per mSWAT, after completing the End of Treatment assessments
- Disease progression per mSWAT during active follow-up
- Withdrawal of consent
- Participant is lost to follow-up. All attempts to contact the participant must be documented.
- At the discretion of the investigator for safety, behavioral, study termination or administrative reasons

Documentation of the reason for discontinuing study participation and the date effective should be made in the Electronic Health Record/medical record and appropriate eCRF

5.9 Prohibited and Concomitant Therapies/Medications

5.9.1 Allowed concomitant medications

Concomitant medications and treatments that are permitted while on study treatment include allopurinol, anti-emetics, anti-diarrheals, FDA-approved bisphosphonates, erythropoietin, transfusions (as necessary), and palliative radiation.

Concurrent treatment with any other anti-neoplastic therapies will not be permitted while on study treatment. Concurrent administration of live vaccines will not be permitted while on study treatment.

During cycle 1 only: Transfusions are not permitted unless platelets <25,000/mm³ or platelets < 50,000/ mm³ accompanied by bleeding. Growth factors are not permitted unless ANC <500/ mm³.

If concomitant therapy must be added or changed, including over-the-counter medications or alternative therapies, the reason and name of the agent/therapy should be recorded in the eCRF and documented in the Electronic Health Record/medical record.

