3.1 Inclusion Criteria

Informed Consent

- ___ 1. Documented informed consent of the participant and/or legally authorized representative.
 - Assent, when appropriate, will be obtained per institutional guidelines

Age Criteria, Performance status

- ___ 2. Age: ≥ 18 years
- ___ 3. Patients must have a life expectancy of > 3 months
- ___ 4. ECOG ≤ 2

Nature of Illness and Illness Related Criteria

- ___ 5. Patients must have a diagnosis of cutaneous CD30+LYPD
- ___ 6. Patients must be relapsed or are refractory to at least 1 prior line of therapy
- ___ 7. At least 2 weeks from prior therapy to time of start of treatment. Prior therapy includes steroids (except prednisone or equivalent – up to 10 mg/day is allowed).

Clinical Laboratory and Organ Function Criteria (To be performed within 21 days prior to Day 1 of protocol therapy unless otherwise stated [see Section 10.0])

 ___ 8. ANC $\geq 1000/\text{mm}^3$ NOTE: Growth factor is not permitted within 14 days of ANC assessment unless cytopenia is secondary to disease involvement. 	ANC: 	Date:

 ___ 9. Platelets $\geq 50,000/\text{mm}^3$ NOTE: Platelet transfusions are not permitted within 14 days of platelet assessment unless cytopenia is secondary to disease involvement. 	Plts: 	Date:

 ___ 10. ___ 10. Total bilirubin $\leq 1.5 \times \text{ULN}$ (unless has Gilbert's disease) 	ULN: Bil: 	Date:

 ___ 11. AST $\leq 2.0 \times \text{ULN}$ 	ULN: AST: 	Date:

 ___ 12. ALT $\leq 2.0 \times \text{ULN}$ 	ULN: ALT: 	Date:

 ___ 13. Creatinine clearance of $\geq 30 \text{ mL/min}$ per 24 hour urine test or the Cockcroft-Gault formula or $\text{CrCl (mL/min)} = \frac{(140-\text{age}) \times \text{actual body weight (kg)}}{72 \times \text{serum creatinine (mg/dL)}} \times 0.85 \text{ for females}$ 
Or
 $\text{CrCl (mL/min)} = \frac{(140-\text{age}) \times \text{actual body weight (kg)}}{0.8136 \times \text{serum creatinine (umol/L)}} \times 0.85 \text{ for females}$ 	Serum Cr: Cr Clearance: 	Date:

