3.2 Exclusion Criteria

Prospective participants who meet any of the following criteria will not be eligible for admission into the study:

Concomitant medications

- ___ 1. Current or planned use of other investigational agents, or concurrent biological, chemotherapy, or radiation therapy during the study treatment period. (See inclusion criterion #7 for washout times).
- ___ 2. Current or planned growth factor or transfusion support. If growth factor or transfusion support is provided between screening and start of treatment, the participant will no longer be eligible.

Other illnesses or conditions

- ___ 3. Prior Allogeneic transplant.
- ___ 4. Acute active infection requiring systemic therapy within 2 weeks prior to enrollment.
- ___ 5. Known history of hepatitis B or hepatitis C infection
- ___ 6. Known HIV infection.
- ___ 7. History of allergic reactions attributed to compounds of similar chemical or biologic composition to leflunomide or cholestyramine.
- ___ 8. Non-hematologic malignancy within the past 3 years aside from the following exceptions:
 - adequately treated basal cell or squamous cell skin cancer
 - carcinoma in situ of the cervix
 - prostate cancer < Gleason Grade 6 with a stable PSA
 - successfully treated in situ carcinoma of the breast

___9. Clinically significant medical disease or condition that, in the investigator's opinion, may interfere with protocol adherence or the patient's ability to give informed consent.

___10. Pregnant women and women who are lactating. Leflunomide has potential for teratogenic or abortifacient effects. Because there is a potential risk for adverse events in nursing infants secondary to treatment of the mother with these agents, breastfeeding should be discontinued if the mother is enrolled on this study.

___11. Any other condition that would, in the Investigator's judgment, contraindicate the patient's participation in the clinical study due to safety concerns or compliance with clinical study procedures, e.g., infection/inflammation, intestinal obstruction, unable to swallow medication, social/ psychological issues, etc.

Noncompliance

___12. Prospective participants who, in the opinion of the investigator, may not be able to comply with all study procedures (including compliance issues related to feasibility/logistics).

Eligibility Confirmed* by (Choose as applicable):	Print Name	Signature	Date
 Site PI			
 Authorized study MD			

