5.9.2 Prohibited medications

- Exposure to any new immunosuppressive medication in the 4 weeks prior to enrollment.
- Patients may not be receiving any other parenteral investigational agents. Oral chemotherapeutic agents or biologics –for example ruxolitinib, rituxan, ibrutinib therapy (either past or current exposure) - is allowed.
- The use of medication that are CYP1A2 inducers and CYP2C8 inhibitors and vitamin K antagonists are prohibited.

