5.10 Supportive care

With the exception of prohibited therapies, participants should receive prophylactic or supportive as clinically indicated per institutional policies.

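### Read literally, the Cycle 1 transfusion rule in Section 5.9.1 bars red cells as well as platelets over most of the platelet range; it was probably meant for platelet transfusions only

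*Combined protocol and SAP*

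**What the plan says.** Section 5.9.1 (Allowed concomitant medications) opens with a list of treatments permitted on study, which includes "erythropoietin, transfusions (as necessary), and palliative radiation". Two restrictions for the first cycle follow in the same section. The first is "During cycle 1 only: Transfusions are not permitted unless platelets <25,000/mm³ or platelets < 50,000/ mm³ accompanied by bleeding". The second is "Growth factors are not permitted unless ANC <500/ mm³".

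Other text bears on how the first restriction should be read:

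- **Section 3.1, criterion 9** requires platelets of at least 50,000/mm³ at screening and adds a note: "Platelet transfusions are not permitted within 14 days of platelet assessment". Here the product is named.
- **Section 3.2, criterion 2** excludes "Current or planned growth factor or transfusion support", and also removes anyone transfused between screening and the start of treatment.
- **Section 5.9.2** (Prohibited medications) does not mention transfusion.
- **Section 5.10** says "With the exception of prohibited therapies, participants should receive prophylactic or supportive as clinically indicated".
- **Section 15.0** accepts departures needed to remove an immediate hazard, but handles them as deviations.
- **Section 6.1** lists both anaemia and melena as expected leflunomide toxicities.

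**The concern.** The Cycle 1 sentence is specific and comes after the general permission, so on an ordinary reading it overrides that permission for the first 28 days. Because it speaks of transfusions without naming a product, it covers red cells. Because its triggers are platelet counts, nothing in it responds to haemoglobin or to bleeding at an adequate platelet count. A patient with symptomatic anaemia, or one bleeding at 60,000/mm³, could not be given red cells without a deviation, whereas a patient at 20,000/mm³ who is not bleeding could receive any product.

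This is an operative instruction about patient care. If staff follow it exactly, the foreseeable results are a reportable deviation or a delayed transfusion. It does not affect the efficacy analysis.

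**Working it through.** No stated statistical figure is involved, so the check is one of logic and scope.

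**Step 1. The rule as written** (Section 5.9.1, Cycle 1). A transfusion is permitted if platelets are <25,000/mm³, or if platelets are <50,000/mm³ and there is bleeding. Applied to three platelet bands, each with and without bleeding:

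| Platelets (/mm³) | Bleeding | No bleeding |
|---|---|---|
| <25,000 | permitted | permitted |
| 25,000 to <50,000 | permitted | barred |
| 50,000 or more | barred | barred |

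Three of the six states are barred. Evaluating the rule at counts from 10,000 to 200,000/mm³, including values at and just below each threshold, gives the same pattern. The six-way count describes the reach of the wording; it is not a probability.

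**Step 2. Where patients start.** Criterion 9 sets a floor of 50,000/mm³, so at the eligibility test all 12 to 14 patients are in the bottom row, where the literal rule gives no route to red cells. The laboratory criteria in Section 3.1 set floors for ANC and platelets but none for haemoglobin, so an anaemic patient with no current or planned transfusion support can enrol.

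**Step 3. What was probably meant.** Four features point to platelet transfusion:

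1. Both triggers are platelet counts.
2. The companion sentence ties growth factors to ANC, again matching the support to the cell line.
3. Criterion 9 names platelet transfusion when that is the product intended.
4. The triggers match two thrombocytopenia rows of Table 7.1.1: Grade 4 (<25 × 10⁹/L, which is <25,000/mm³) and Grade 3 with bleeding (25 to <50 × 10⁹/L, which is 25,000 to <50,000/mm³). Both rows call for a hold and supportive care.

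**Step 4. Whether other text restores red cells.**

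- *Section 5.10* supports care as indicated but excepts prohibited therapies. Section 5.9.2 does not list transfusion, while Section 5.9.1 says it is not permitted, so 5.10 can be read either way.
- *Section 15.0* covers an immediate hazard, but only as a deviation, and it does not plainly reach anaemia that is symptomatic without being an immediate hazard.
- *Section 3.2, criterion 2* stops at the start of treatment and does not address a need that arises after the first dose.
- *Table 7.1.1* has no anaemia row, so it gives no alternative instruction.

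**Step 5. Size.**

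- Share of maximum treatment time: 28 / (13 × 28) = 28 / 364 = 7.7%.
- The documents give no rate of red-cell transfusion. The Section 6.1 legend puts unmarked events, which include anaemia, at 1% to 3% of patients. If that carried over to this population, expected anaemia cases of any grade would run from 12 × 0.01 = 0.12 to 14 × 0.03 = 0.42. Cases that need red cells, within 28 days and in a barred state, would be a subset of these.

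**The case against.** The strongest reply is that no sensible clinician would take a platelet trigger to govern red cells. The same thresholds appear in the thrombocytopenia rows of Table 7.1.1, so in context the sentence reads as a platelet-support rule with an adjective missing. The general allowance, the absence of transfusion from Section 5.9.2, the supportive-care clause in 5.10 and the hazard provision in Section 15.0 together leave room to transfuse. Anaemia and melena are both in the infrequent category of Section 6.1, and patients with current or planned transfusion support are excluded. On this view the point is editorial.

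Much of this stands. The intended meaning is fairly clear, many clinicians would transfuse anyway, and the expected number of affected patients is well below one on the Section 6.1 figures. Counting barred states says nothing about frequency, and a delayed transfusion is a possibility, not a prediction.

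The conclusion that the text can stay does not follow. Evidence that a platelet rule was meant is evidence that the words used are wrong. The softening provisions leave an ambiguity or classify the transfusion as a deviation; none clearly permits red cells.

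**Conclusion.** The concern holds. As written, the Cycle 1 rule bars red-cell transfusion at platelets of 50,000/mm³ or more, and at 25,000 to <50,000/mm³ without bleeding. That reading follows from the text alone. That platelet transfusion was intended is an inference, a well-supported one; a deliberate ban on all products is possible but implausible, and the documents give no reason for one.

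The matter is a minor safety-wording correction, confined to one cycle, and may never affect a patient in this trial. The frequency estimate assumes that the Section 6.1 incidence applies to these patients. No endpoint, sample-size figure or analysis changes. The correction should still be made, because the sentence governs care and is wrong as it stands.

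**What to change.** In Section 5.9.1, begin the Cycle 1 restriction with *Platelet transfusions* in place of *Transfusions*, keeping the existing triggers. Then add: *Red-cell transfusion is permitted as clinically necessary in all cycles.* Once the product is named, red cells already fall under the general allowance, so the added sentence is not strictly needed; it removes any remaining doubt.

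The cost is one word and one short sentence. No visits, procedures or data items are added.

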5.9.2 Prohibited medications

- Exposure to any new immunosuppressive medication in the 4 weeks prior to enrollment.
- Patients may not be receiving any other parenteral investigational agents. Oral chemotherapeutic agents or biologics –for example ruxolitinib, rituxan, ibrutinib therapy (either past or current exposure) - is allowed.
- The use of medication that are CYP1A2 inducers and CYP2C8 inhibitors and vitamin K antagonists are prohibited.

5.10 Supportive care

With the exception of prohibited therapies, participants should receive prophylactic or supportive as clinically indicated per institutional policies.

6.0 ANTICIPATED ADVERSE EVENT LIST

6.1 Leflunomide

Per the package insert for leflunomide, the expected toxicities for leflunomide follow, where the asterisk (*) signifies a common event (10%-30% of patients), unmarked items are infrequent events (1-3% of patients), a double asterisk (**) signifies a rare but possibly serious event, and a triple asterisk (***) signifies an event that may become serious and occurs in up to 10% of patients:

Blood and lymphatic system	anemia (including iron deficiency anemia), ecchymosis, pancytopenia**, agranulocytosis**, neutropenia**, thrombocytopenia**, leukopenia**
Cardiac	angina pectoris, migraine, palpitation, tachycardia, vasodilatation

Endocrine	diabetes mellitus, hyperthyroidism
Eye	blurred vision, cataract, conjunctivitis, eye disorder
Gastrointestinal	diarrhea*, abdominal pain, dyspepsia, nausea, vomiting, oral ulceration, anorexia, pancreatitis**, constipation, esophagitis, flatulence, gastritis, gingivitis, melena, oral moniliasis, pharyngitis, salivary gland enlarged, stomatitis (or aphthous stomatitis), tooth disorder
Hepatobiliary	cirrhosis**, hepatitis**, hepatic failure**, acute hepatic necrosis**, cholelithiasis**, cholestasis**, elevated hepatic enzymes (primarily ALT and AST)
Immune system	allergic reactions, anaphylactoid reactions**
Infections	respiratory infection*, infections (including bronchitis, rhinitis, sinusitis, pharyngitis, pneumonia, and urinary tract infections, oral or vaginal candidiasis, herpes simplex, herpes zoster, and fungal dermatitis), opportunistic and/or severe infections** including sepsis, that may be fatal (especially Pneumocystis jiroveci pneumonia, tuberculosis, aspergillosis)
Metabolism and nutrition	hyperglycemia, creatine phosphokinase increased, hyperlipidemia
Musculoskeletal and connective tissue	arthrosis, bone necrosis, bone pain, bursitis, muscle cramps, myalgia, tendon rupture
Neoplasms	secondary malignancy**, cyst
Nervous system	headache*, peripheral neuropathy* (including peripheral numbness, tingling, burning, severe pain, cold sensation in the distal extremities, or extremity weakness), paresthesias, taste perversion (dysgeusia), anxiety, depression, dry mouth, insomnia, neuralgia, neuritis, sleep disorder, sweating increased, vertigo, migraine
Renal and urinary	albuminuria, cystitis, dysuria, hematuria, hypophosphaturia, hyperuricemia, increased urinary frequency
Reproductive	menstrual irregularity/disorder, menstrual disorder, vaginal moniliasis vaginal moniliasis, prostate disorder
Respiratory	interstitial lung disease** (sometimes fatal), interstitial pneumonitis**, pulmonary fibrosis**, asthma, dyspnea, epistaxis, lung disorder
Skin and subcutaneous tissue	maculopapular rash*, dry skin*, alopecia*, hair discoloration*, Stevens-Johnson syndrome**, toxic epidermal necrolysis**, erythema multiforme**, cutaneous lupus erythematosus**, acne, contact dermatitis, fungal dermatitis, hematoma, nail disorder, skin discoloration, skin disorder, skin nodule, subcutaneous nodule, skin ulcer
Vascular	varicose veins, hypertension***, vasculitis, cutaneous necrotizing vasculitis**
Miscellaneous	weight loss*, leg cramps*, jaundice**, allergy related angioedema**, fever, peripheral edema, hernia, neck pain, pelvic pain, pain, abscess, malaise

6.2 Cholestyramine

Per the package insert for cholestyramine, the expected toxicities for cholestyramine follow, where the double asterisk (**) signifies a common event, and a single asterisk (*) signifies a less common event, and remaining unmarked items are less likely:

Blood and lymphatic system	anemia, ecchymosis, prolonged prothrombin time, hypoprothrombinemia
Ear and labyrinth	tinnitus, vertigo
Eye	uveitis
Gastrointestinal	constipation**, abdominal pain*, anorexia*, nausea*, vomiting*, diarrhea*, flatulence*, diarrhea*, eructation, * steatorrhea, * diverticulitis, bleeding from known duodenal ulcer, dysphagia, gastrointestinal hemorrhage, hemorrhoidal bleeding, hiccups, intestinal obstruction (rare), melena, pancreatitis, rectal pain, tongue irritation, tooth enamel damage (dental erosion), dental bleeding, dental caries, dental discoloration

Hepatobiliary	abnormal hepatic function tests, biliary colic, gallbladder calcification
Immune system	hypersensitivity reaction
Infections	
Metabolism and nutrition	hyperchloremic metabolic acidosis
Musculoskeletal and connective tissue	arthralgia, arthritis, backache, myalgia, osteoporosis associated with vitamin D deficiency
Nervous system	anxiety, dizziness, drowsiness, dysgeusia, fatigue, headache, neuralgia, paresthesia, syncope
Renal and urinary	hematuria, dysuria, burnt odor to urine, diuresis
Respiratory	asthma dyspnea and wheezing associated with hypersensitivity reaction
Skin and subcutaneous tissue	perianal skin irritation, skin irritation, skin rash, urticaria
Miscellaneous	adenopathy, increased libido, edema, bleeding tendencies due to vitamin K deficiency, vitamin deficiency (A, D, E, K), weight loss, weight gain, hematoma, hemorrhage, femoral nerve pain

7.0 DOSE DELAY/MODIFICATION GUIDELINES

7.1 Dose Modifications for Leflunomide

7.1.1 General Information

- a. The study will use the NCI Common Terminology Criteria for Adverse Events (CTCAE) version 5.0 to grade toxicities. A copy of the version 5.0 can be downloaded from:
<http://evs.nci.nih.gov/ftp1/CTCAE/About.html>
- b. Rules for dose modification are found in Table 7.1.1.
- c. Baseline values are from the last values obtained prior to treatment.
- d. **For holds due to toxicities related to study agent, if the participant does not meet criteria to resume treatment within 14 days, the participant must permanently discontinue study treatment.**

7.1.2 Dose Modifications

The tables below detail the specific dose modifications for toxicities on single agent leflunomide (Table 7.1.1) and are to be used in agreement with the information in [Section 7.1.1](#).

Table 7.1.1 Dose Modifications for Leflunomide Treatment

Adverse Event	Treatment modification
Hematological Toxicities:	
Febrile Neutropenia Grade 3 (ANC: $<1.0 \times 10^9/L$ with a single temperature of $>38.3^{\circ}C$ or a sustained temperature $\geq 38.0^{\circ}C$ for more than one hour.	
At 20 mg:
 
 ○ Hold study agent. ○ If resolves to $ANC \geq 1.0 \times 10^9/L$ and temperature $< 38.0^{\circ}C$ within 14 days, resume study agent at 10 mg. ○ If does not resolve within 14 days, permanently discontinue study agent. 
At 10 mg: Permanently discontinue study agent

Febrile Neutropenia Grade 4 Life threatening consequences; urgent intervention needed.	Permanently discontinue study agent.
Neutropenia (ANC) Grade 1 ($1.5 \times 10^9/L < LLN$)	Maintain study agent.

Neutropenia (ANC) Grade 2 (1.0 –<1.5x 10 ⁹ /L)	Maintain study agent.
Neutropenia (ANC) Grade 3 (0.5 –< 1.0x 10 ⁹ /L)	Maintain study agent. Growth factor recommended after cycle 1.
Neutropenia (ANC) Grade 4 (<0.5x 10 ⁹ /L)	
At 20 mg:
 
 ○ Hold study agent and provide supportive care. ○ If ANC does not resolve to ≤ grade 3 (ANC ≥ 0.5 x 10⁹/L) in 5 days, permanently discontinue study agent. Otherwise proceed as follows: ○ If resolves to ≤ grade 2 (ANC ≥ 1.0 x 10⁹/L) in ≤ 14 days, resume study agent at 10 mg. ○ If ANC does not resolve to ≤ grade 2 (ANC ≥ 1.0 x 10⁹/L) by 14 days, permanently discontinue study agent. 
At 10 mg: Permanently discontinue study agent.

Thrombocytopenia Grade 1 (75 x 10 ⁹ /L -<LLN)	Maintain study agent
Thrombocytopenia Grade 2 (50 –<75 x 10 ⁹ /L)	Maintain study agent
Thrombocytopenia Grade 3 without bleeding (25 –<50 x 10 ⁹ /L)	Maintain study agent.
Thrombocytopenia Grade 3 with bleeding (25 –<50 x 10 ⁹ /L)	
At 20 mg:
 
 ○ Hold study agent and provide supportive care. ○ If bleeding does not resolve in 5 days, permanently discontinue study agent. Otherwise proceed as follows: ○ If bleeding resolves within 5 days and platelets resolve to ≤ grade 2 (platelets ≥ 50 x 10⁹/L) in ≤ 14 days, resume study agent 10 mg. ○ If bleeding resolves within 5 days but thrombocytopenia does not resolve to ≤ grade 2 (platelets ≥ 50 x 10⁹/L) by 14 days, permanently discontinue study agent. 
At 10 mg: Permanently discontinue study agent.

Thrombocytopenia Grade 4 (<25 x 10 ⁹ /L)	
At 20 mg:
 
 ○ Hold study agent and provide supportive care. ○ If platelets do not resolve to ≤ grade 3 (platelets ≥ 25 x 10⁹/L) in 5 days, permanently discontinue study agent. Otherwise proceed as follows: ○ If resolves to ≤ grade 2 (platelets ≥ 50 x 10⁹/L) in ≤ 14 days, resume study agent 10 mg. ○ If thrombocytopenia does not resolve to ≤ grade 2 (platelets ≥ 50 x 10⁹/L) by 14 days, permanently discontinue study agent. 
At 10 mg: permanently discontinue study agent.

Gastrointestinal	
Diarrhea Grade 1 (2-3 stools/day >baseline)	Maintain treatment.
Diarrhea Grade 2 (4-6 stools/day > baseline)	Maintain study agent.
Diarrhea Grade 3 (7-9 stools/day > baseline)	
At 20 mg:
 
Hold study agent and provide optimal anti-diarrheal therapy.
 
First Occurrence:
 
 If resolves to ≤ grade 1 in ≤ 7 days, resume at 20 mg. If resolves to ≤ grade 1 in 8-14 days, resume study agent at 10 mg. If does not resolve within 14 days, permanently discontinue study agent. 
Recurrence:
 
 If resolves to ≤ grade 1 in ≤ 14 days, resume at 10 mg. If does not resolve within 14 days, permanently discontinue study agent. 
At 10 mg: Permanently discontinue study agent.

Diarrhea Grade 4 (≥10 stools/day > baseline)	
At 20 mg:
 
Hold study agent and provide optimal anti-diarrheal therapy.
 
If does not resolve to Grade 3 within 48 hours, permanently discontinue study agent.
 
If resolves to Grade 3 within 48 hours, then:
 
First Occurrence:
 
 Hold until resolution to ≤ grade 1. If resolved in ≤ 7 days, resume at pre-hold dose. If resolved in 8-14 days, resume study agent at 10 mg. If not resolved within 14 days, permanently discontinue study agent. 
Recurrence:
 
 Hold until resolution to ≤ grade 1. If resolved in ≤ 14 days, resume study agent at 10 mg. If not resolved within 14 days, permanently discontinue study agent. 
At 10 mg: Permanently discontinue study agent.

Vomiting or Nausea Grade 1	Maintain study agent.
Vomiting or Nausea Grade 2	Maintain study agent.
Vomiting or Nausea Grade 3	
At 20 mg:
 
Hold study agent and provide optimal supportive care/therapy.
 
First Occurrence:
 
 If resolves to ≤ grade 1 in ≤ 7 days, resume at pre-hold dose. If resolves to ≤ grade 1 in 8-14 days, resume study agent at 10 mg. If does not resolve within 14 days, permanently discontinue study agent. 
Recurrence:
 
 If resolves to ≤ grade 1 in ≤ 14 days, resume at 10 mg. If does not resolve within 14 days, permanently discontinue study agent. 
At 10 mg: Permanently discontinue study agent.

Vomiting Grade 4	
At 20 mg:
 
Hold study agent and provide optimal supportive care/therapy.
 
If does not resolve to Grade 3 within 48 hours, permanently discontinue study agent.
 
If resolves to Grade 3 within 48 hours, then:
 
First Occurrence:
 
 Hold until resolution to ≤ grade 1. If resolved in ≤ 7 days, resume at pre-hold dose. If resolved in 8-14 days, resume study agent at 10 mg. If not resolved within 14 days, permanently discontinue study agent. 
Recurrence:
 
 Hold until resolution to ≤ grade 1. If resolved in ≤ 14 days, resume study agent at 10 mg. If not resolved within 14 days, permanently discontinue study agent. 
At 10 mg: Permanently discontinue study agent.

Hepatic investigations	
ALT (SGPT) or AST (SGOT) ≤ 3.0 x ULN or TBili ≤ 1.5 x ULN	Maintain study agent.
ALT (SGPT) or AST (SGOT) >3.0 - 5.0 x ULN or TBili >1.5 - ≥ 3.0 x ULN	
First Occurrence:
 
Hold until resolution to < 3.0 x ULN for ALT or AST or < 1.5 for TBili. Resume at pre-hold dose if resolved within 14 days. If does not resolve within 14 days, permanently discontinue study agent.
 
Recurrence:
 
Hold until resolution to < 3.0 x ULN for ALT or AST or <1.5 for TBili. Resume at 10 mg if resolved within 14 days. If does not resolve within 14 days, permanently discontinue study agent.

ALT (SGPT) or AST (SGOT) > 5.0 x ULN or TBili > 3.0 x ULN	Permanently discontinue study agent.
Electrolyte/metabolic toxicity	
Electrolyte/metabolic Grade 3	
Provide support care. Maintain study agent per investigator discretion.
 
If alteration persists despite aggressive replacement therapy, then dose reduce or permanently discontinue (per investigator discretion with PI consultation).

Electrolyte/metabolic Grade 4	
Provide support care. Maintain study agent per investigator discretion.
 
If resolves to Grade 1 or baseline within 48: for first event, maintain at pre-hold dose; for recurrent event, dose reduce or permanently discontinue (per investigator discretion with PI consultation).
 
If does not resolve to Grade 1 or baseline within 48 hours, permanently discontinue study agent.

Other unspecified Non-Hem toxicities considered related to leflunomide	
Grade 1	Maintain study agent.
Grade 2	Maintain study agent.
Grade 3	
First Occurrence:
 
Hold until resolution to ≤ Grade 2. Resume at pre-hold dose if resolved within 7 days. If does not resolve within 7 days, permanently discontinue study agent.
 
Recurrence:
 
Hold until resolution to ≤ Grade 1. Resume at 10 mg if resolved within 14 days. If does not resolve within 14 days, permanently discontinue study agent.

Grade 4	Permanently discontinue study agent.
Other unspecified Non-Hem Toxicities considered UNRELATED to study agent	
Other unspecified events of any grade considered unlikely to be related or not related to study agents.	Maintain treatment with study agents. Interruption of study agent or dose de-escalation is permitted if the investigator consults with the Principal Investigator to determine that this is in the best interest of the participant.

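### Table 7.1.1, 20 mg: the Thrombocytopenia Grade 4 row has no bleeding condition for restart, so in a narrow set of cases leflunomide could resume during bleeding

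*Combined protocol and SAP*

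**What the plan says.** All of this concerns a patient on 20 mg. At 10 mg both platelet rows stop the drug permanently.

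- **Thrombocytopenia Grade 4 (<25 × 10⁹/L), Section 7.1.2.** Leflunomide is held with supportive care. It is stopped for good if platelets have not reached 25 within 5 days, or 50 by 14 days. Otherwise: "If resolves to ≤ grade 2 (platelets ≥ 50 x 10⁹/L) in ≤ 14 days, resume study agent 10 mg". Bleeding is not mentioned.
- **Thrombocytopenia Grade 3 with bleeding (25 to <50 × 10⁹/L), same table.** "If bleeding does not resolve in 5 days, permanently discontinue study agent". Restart at 10 mg needs both bleeding resolved within 5 days and platelets of at least 50 within 14 days.
- **Catch-all for related events.** Under "Other unspecified Non-Hem toxicities considered related to leflunomide", Grades 1 and 2 continue treatment and Grade 4 is a permanent stop. For a first Grade 3 event: "Hold until resolution to ≤ Grade 2. Resume at pre-hold dose if resolved within 7 days"; if that is not met in 7 days, the drug is stopped. A recurrent Grade 3 event is held until Grade 1 or better, with a 14-day limit.
- **Catch-all for unrelated events.** For "Other unspecified events of any grade considered unlikely to be related or not related to study agents", treatment continues. Interruption is optional after consultation with the Principal Investigator.
- **Section 7.1.1, item d.** For holds due to related toxicity: "if the participant does not meet criteria to resume treatment within 14 days, the participant must permanently discontinue study treatment". This sets a time limit on whatever resume criteria apply and adds none about bleeding.
- **Section 5.6** allows removal when the treating investigator judges a patient unfit for further treatment.

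**The concern.** The two platelet rows run in the wrong order of severity. For a patient at 25 to <50 × 10⁹/L, bleeding that lasts beyond 5 days ends treatment. For a patient below 25, the row that governs the hold never asks about bleeding and directs a restart once the count reaches 50. Grade 3 is divided by bleeding status and Grade 4 is not, and nothing in the protocol explains why the more severe grade should have the weaker release rule.

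What is at stake is patient safety in a single-arm pilot. A drug for which Section 6.1 lists thrombocytopenia could be restarted, on the table's own instruction, while the patient is still bleeding. The half-life of the active metabolite is about 2 weeks (Sections 2.2 and 8.1.4), so an early restart adds to substantial residual exposure.

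**Working it through.** There is no sample-size, power or error-rate figure to reproduce. The check is to set the rows side by side and follow them by day. Days count from the start of the hold, and the patient is on 20 mg. The thresholds are those printed in Table 7.1.1; the patient values are illustrative assumptions.

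**Step 1. The two rows compared.**

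| Condition | Grade 3 with bleeding | Grade 4 |
|---|---|---|
| 5-day test | bleeding resolved | platelets ≥25 |
| Restart at 10 mg | bleeding resolved within 5 days and platelets ≥50 within 14 days | platelets ≥50 within 14 days |
| Bleeding still present at Day 5 | permanent stop | not addressed |

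**Step 2. What the catch-all rows remove.** This assumes bleeding is recorded as a non-hematologic event. Section 6.1 supports that in part: it lists epistaxis, hematuria and melena under organ systems other than blood. I apply the Grade 4 platelet row and the catch-all together and follow the stricter action, which is the reading kindest to the plan.

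Case 1: platelets 20 on Day 0 and 55 on Day 5, no count recorded at 25 to <50, bleeding from Day 0 to Day 8. The Grade 4 row's tests are met, since 55 ≥ 25 by Day 5 and 55 ≥ 50 by Day 14. Taken alone, it restarts at 10 mg on Day 5.

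| Bleeding in Case 1 | Combined result |
|---|---|
| Related, Grade 4 | permanent stop, Day 0 |
| Related, first occurrence, Grade 3 throughout | not at Grade 2 by Day 0 + 7, so permanent stop, Day 7 |
| Related, first occurrence, Grade 3 falling to Grade 2 on Day 4 | catch-all hold released (4 ≤ 7); restart at 10 mg on Day 5, still bleeding |
| Related, Grade 1–2 | restart at 10 mg on Day 5, still bleeding |
| Judged unrelated, any grade | restart at 10 mg on Day 5, still bleeding, unless the investigator and Principal Investigator choose to interrupt |

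In the last three lines, bleeding continues for 8 − 5 = 3 days after restart. If the same bleeding starts at platelets of 30, the Grade 3-with-bleeding row stops the drug permanently on Day 0 + 5 = Day 5.

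**Step 3. What the Grade 3-with-bleeding row removes.** Case 2: platelets 20 on Day 0, 30 on Day 4 and 55 on Day 10, with bleeding to Day 12. The Grade 4 row alone would restart on Day 10. On Day 4, however, the patient is bleeding with a count of 30, which fits the definition of the Grade 3-with-bleeding row. Even if its 5 days are counted from Day 4, the stop falls on Day 4 + 5 = Day 9, before Day 10. The table does not say that rows are re-applied during recovery, or when that clock starts, but the reading is reasonable. I do not count Case 2 in the gap.

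**Step 4. What is left.** For bleeding present throughout the hold, the recorded count must pass from <25 to ≥50 with nothing recorded between. Because the Grade 4 row needs ≥25 by Day 5, the first recorded recovery must then be ≥50 on or before Day 5. Transfusion is a plausible route: the row calls for supportive care, and Section 5.9.1 permits transfusion, even in Cycle 1, when platelets are below 25,000/mm³. Inclusion criterion 9 generally bars platelet transfusion within 14 days of the eligibility count; the restart threshold has no such safeguard.

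**The case against.** The strongest defence is that the table is coherent without a bleeding term in the Grade 4 row. Bleeding divides Grade 3 because a Grade 3 patient who is not bleeding continues treatment. At Grade 4 everyone is held, so no division is needed to trigger the hold. Release at ≥50 matches the Grade 1 and Grade 2 rows, which continue treatment at that level with no bleeding condition, and here release is at half the dose. That explains the hold. It does not explain the release: the Grade 3-with-bleeding row uses the same ≥50 threshold, also at 10 mg, and still requires bleeding to have resolved.

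A second defence is that other provisions already protect the patient. Much of this stands. The catch-all rows cover the most serious related bleeding, the Grade 3-with-bleeding row can reach a patient recovering through 25 to <50, and Section 5.6 gives the investigator authority to remove a patient. But Section 5.6 is discretion, which exists equally for Grade 3, where an explicit rule was still written.

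A third objection concerns the remedy. A 5-day limit counted only from the start of the hold would penalise a short bleed that begins late: one running from Day 4 to Day 7 would force a stop on Day 5. The skin biopsies in Section 9.2 are a possible source of such minor bleeding. This is correct, and the wording below allows for it.

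A reader might infer that any patient with Grade 4 thrombocytopenia who is bleeding would be restarted. The documents do not support that, for the reasons in Steps 2 and 3.

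**Conclusion.** The point holds in a limited form. At 20 mg the Grade 4 row can direct a restart at 10 mg during bleeding when recorded platelets go from <25 to ≥50 × 10⁹/L and the bleeding is related Grade 1–2, related Grade 3 already down to Grade 2, or judged unrelated. In the same bleeding scenario, the less severe platelet row stops the drug on Day 5.

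Two assumptions set the size of the gap. One is that bleeding falls under the non-hematologic catch-all rows; if it does not, the gap is wider. The other is that a bleeding patient with a recorded count of 25 to <50 is moved to the Grade 3-with-bleeding row; if not, Case 2 also falls in the gap.

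Section 6.1 marks thrombocytopenia as rare and gives no rate, so I attach no probability. The primary endpoint's definition and analysis do not depend on this row. The change should be made because it aligns the more severe grade with the protocol's own standard at little cost. It is not a reason to question the trial.

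**What to change.** Add to the Thrombocytopenia Grade 4 row, at 20 mg: *If bleeding is present, resume at 10 mg only if bleeding has also resolved; if bleeding does not resolve within 5 days of the later of the start of the hold or the onset of bleeding, permanently discontinue study agent.*

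Effect on the worked cases:

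- **Case 1, the three open lines:** the limit is Day 0 + 5 = Day 5 and bleeding runs to Day 8, so the drug stops on Day 5, as in the Grade 3-with-bleeding row.
- **Quick recovery** (bleeding from Day 0, platelets 50 on Day 3, bleeding ends Day 4): restart on Day 4 instead of Day 3.
- **Late short bleed** (Day 4 to Day 7): the limit is Day 4 + 5 = Day 9, so the patient is not stopped for bleeding and may restart from Day 7 if platelets are ≥50.

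For related toxicity, the 14-day limit in Section 7.1.1, item d, still caps the hold.

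The cost is one sentence in an amendment, with no extra patients. The 5-day check is already in the row; a bleed that starts later needs its own check. The downside is that a few patients would restart later or stop, as they already would under the Grade 3-with-bleeding row. In a pilot of 12 to 14 patients each such stop matters, but the event is listed as rare.
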